## **7.2 Dose and treatment regimens**

The IP will be administered at the study site on treatment visits and within visit windows as specified in [Table 1](#). A minimum interval of 7 days is required between 2 dosing visits.

### **IP administration**

[figure not shown]
IP will be administered by a qualified, unblinded healthcare professional. The two injections should be administered within the same body location, separated by at least 3 cm. The injection site must be recorded in the source documents at each treatment visit and recorded in the eCRF.

IP must be equilibrated to room temperature for a minimum of 30 minutes prior to dose administration.

The person administering the dose will wipe the skin surface of the upper arm, anterior thigh or abdomen with alcohol, and allow to air dry. The skin will be pinched to isolate the SC tissue from the muscle. The needle will be inserted at a 90-degree angle approximately halfway into the SC tissue. The IP will be slowly injected (at least 5-second duration is recommended) into the SC tissue using gentle pressure. The area should not be massaged after injection.

It is advised that the site of injection of IP be rotated such that the subject receives IP at a different anatomical site at each treatment visit. The suggested injection site rotation sequence is presented below in [Figure 2](#).

**Figure 2**                    **Injection sites and rotation scheme**

In cases when rotation of the injection site is not favorable for the subject and/or Investigator, the injection site, along with the reason why the site was changed, should be recorded in the source documents and eCRF for each such occurrence.

Further details on IP administration are provided in the IP Handling Instructions. IP administration must be carried out according to these instructions.

### **Post IP Administration (Visits 3-6)**

At each visit, the subject will be observed for the appearance of any acute drug reactions, for a minimum of 2 hours with vital signs taken every 30 minutes, until stable.

### **Post IP Administration (Visits 7- 28)**

At each visit, the subject will be observed for the appearance of any acute drug reactions, for a minimum of 1 hour with vital signs taken every 30 minutes, until stable.

### **Conditions requiring IP administration rescheduling**

If any of the following should occur, the Investigator should reschedule the visit and IP should not be administered until the rescheduled visit:

- The subject has an intercurrent illness, that in the opinion of the Investigator may compromise the safety of the subject in the study (e.g., viral illnesses)
- The subject, in the opinion of the Investigator, is experiencing an acute or emerging asthma exacerbation
- The subject is febrile (defined as  $\geq 38^{\circ}\text{C}$ ;  $\geq 100.4^{\circ}\text{F}$ ) within 72 hours prior to IP administration

### **7.3 Labelling**

Labelling of the IP will be carried out by AstraZeneca or designee in accordance with Annex 13 and current Good Manufacturing Practice (GMP) and regulatory requirements of each country participating in the study. The labels will be translated into local languages where applicable and required by local regulations.

### **7.4 Storage**

Tralokinumab/placebo is to be stored at the study site in a secured facility with limited access and controlled temperature. The temperature should be monitored on daily basis and documented in the temperature monitoring log.

The IP must be kept in the original outer container and under conditions specified on the label.

In the following cases:

- Temperature excursion upon receipt or during storage at the study site
- Damaged kit upon receipt, or
- Damaged syringe/cartridge,

Site staff should not use the affected IP, and should immediately contact their AstraZeneca representative for further guidance. Damaged IP should be documented via IWRS/IVRS (please refer to the IWRS/IVRS manual for further details).

### **7.5 Compliance**

The date and time of all IP administrations, as well as any missed doses, should be recorded in the appropriate section of the eCRF.

## 7.6 Accountability

The study drugs provided for this study will be used only as directed in the protocol.

It is the investigator's responsibility to ensure that a procedure is established and maintained for the operation of the unblinded study drugs, this includes but is not limited to:

- The study drugs are administered only by a qualified, unblinded health professional named in the delegation of responsibility log.
- An unblinded health professional will account for all study drugs dispensed to the subjects.

An unblinded health professional, if applicable, or the blinded AstraZeneca monitor will account for all study drugs received at the site, unused study drugs and for appropriate destruction. Certificates of delivery and destruction should be signed.

In case of malfunctioning APFS, the centre should contact the unblinded AstraZeneca monitor to initiate a product complaint process according to applicable guidelines.

## 7.7 Concomitant and other treatments

### 7.7.1 Concomitant medications

Information about any treatment in the 3 months prior to the date of the subject's informed consent or assent, and all the concomitant treatments given during the study, with reason for the treatment, will be collected by the Investigator/authorized delegate at each visit (as shown in Table 1) and recorded in the eCRF.

**Note:** to satisfy inclusion criterion 6, the history of continuous treatment with ICS corresponding to  $\geq 500\mu\text{g}$  fluticasone propionate dry powder formulation equivalents plus a LABA for at least 3 months prior to Visit 1 should be documented in source and recorded in the eCRF (see section 4.1.1).

### Maintenance of asthma controller medication

All subjects are required to be treated with a stable dose of ICS corresponding to  $\geq 500\mu\text{g}$  fluticasone propionate dry powder formulation equivalents (as outlined in Appendix F) and LABA for at least 3 months prior to Visit 1 and during the treatment period. Subjects may also receive other physician prescribed asthma controller medications.

The aim of this study is to establish the treatment effect of tralokinumab as an add-on treatment and therefore the maintenance asthma controller therapy should be maintained at a stable dose from Visit 1 until the end of the treatment period, in order to prevent any independent confounding of the anticipated treatment effect of tralokinumab. **Changes to the subject's maintenance asthma controller medication regimen are discouraged during the treatment period**, unless judged medically necessary by the Investigator. Ideally, such changes should be discussed with the AstraZeneca Study Team Physician, prior to any change

being made. All changes in the subject's maintenance medication should be documented in source along with rationale for change and recorded in eCRF.

Maintenance medication is not regarded as an IP, but will be provided/reimbursed by AstraZeneca according to local regulations, in order to maintain appropriate oversight and access to this concomitant therapy.

Subjects on maintenance treatment with theophylline should have a documented blood concentration levels within therapeutic range. If this is not documented before signing the informed consent, it can be obtained after informed consent has been given or as part of the Visit 1 procedures. The sample can be analysed at the central or local lab as applicable.

### **Rescue medication**

Salbutamol, albuterol or levalbuterol will be used as rescue medication during the study in the event of a worsening of asthma symptoms. As with the maintenance ICS-LABA, rescue medication is not regarded as an IP, but will be provided/reimbursed by AstraZeneca according to local regulations, in order to ensure access to essential rescue therapy.

#### **7.7.2 Restrictions during and after the study**

##### **7.7.2.1 Asthma medication restrictions**

##### **Use of short-acting $\beta_2$ -agonists (SABA)**

Regularly scheduled SABA use in the absence of any asthma symptoms is discouraged from enrollment and throughout the study duration.

Prophylactic use of SABA (e.g., prior to planned exercise) if deemed necessary by the subject and the Investigator, may be used, but should **not** be recorded in the Asthma Daily Diary. Any such use should be documented in medical notes and recorded in the eCRF.

SABA via a metered dose device is permitted as needed for worsening asthma symptoms (i.e., rescue use) and will be recorded in the Asthma Daily Diary as number of inhalations.

Rescue use of SABA administered via jet or ultrasonic nebulization is allowed. Occasions where SABA was administered via nebulization will be recorded separately from metered dose inhaler inhalations in the Asthma Daily Diary.

##### **Use of short acting anticholinergics**

The use of short acting anticholinergics (e.g., ipratropium) as a rescue treatment for worsening asthma symptoms outside of managing an asthma exacerbation event is not allowed from enrollment and throughout the study duration.

##### **Use of long-acting $\beta_2$ -agonists (LABA) as a reliever**

The use of LABA as a reliever (e.g., Symbicort maintenance and reliever treatment) is not allowed from enrollment and throughout the study duration.

### **Use of theophylline and once daily bronchodilators**

Use of theophylline and once daily BDs is allowed at the discretion of the Investigator. However use of these drugs should be stabilized at least 3 months prior to the subject entering the study. Also, a 48 hour minimum wash-out period is required before spirometry if a subject is using theophylline or a once-daily BD. Should the subject be taking theophylline or the once daily BD in the evening, it is advised that the Investigator ask the subject to reschedule their theophylline or BD regimen to morning use, if there are no medical reasons to prevent this change.

### **Asthma medication restrictions on the days of scheduled site visit spirometry**

Pre- and/or post-dose spirometry assessments will be performed at the study site at scheduled visits (see [Table 1](#)). Restriction to a subject's maintenance medication is required prior to the spirometry as described below (also see section [5.1.2](#)):

#### **Visits 2 and 3**

Subjects will be asked to withhold their twice daily BD therapy (including ICS-LABA) on the morning of the screening FEV1 measurement and reversibility test for 12–24 hours prior to the assessment for eligibility (see Section 3.1, inclusion criteria 8 and 9). For once daily BDs the required washout is  $\geq 48$  hours. In case the subject does not meet the reversibility eligibility criteria, and a second re-test is done (not earlier than next calendar day and not later than 7 calendar days after the failed attempt), twice daily BDs may be withheld for 24 hours.

#### **Treatment Period (Visits 4-29)**

It is important that a true pre-BD (i.e., trough) FEV1 reading obtained in order to maintain the integrity of planned efficacy analyses around lung function improvement. **Therefore, subjects will be asked to withhold their usual BD and SABA as outlined in the section above for Visits 2 and 3.**

The subject's usual asthma controller medications may be administered, following completion of the pre-BD spirometry. The suggested order of administration of the subject's usual asthma controller, per protocol SABA (on visits where post-BD spirometry is assessed), and IP administration relative to scheduled pre and post-BD spirometry is given in section [5.1.2](#).

If the subject has taken their usual ICS-LABA and/or any other BD without appropriate washout period (see Visits 2 and 3 above) before the site visit, the Investigator/authorized delegate should remind the subject of the importance of withholding their BD for an appropriate time and reschedule the visit for another day, within the allowed window.

If the subject has taken rescue SABA within 6 hours of the planned site visit spirometry they should ideally 1) remain at the site until such time that the 6 hour window has been reached or 2) return on another day, within the visit window. If neither of these options is feasible for the subject, spirometry may be performed with a notation indicating that the pre-BD spirometry was conducted within 6 hours of SABA use.

### **Asthma medication restrictions prior to home PEF testing**

Subjects should avoid taking their morning asthma controller medication prior to the morning home PEF testing, and should conduct the evening home lung function testing before taking evening asthma controller medication. When possible, home PEF testing, should be taken at least 6 hours after the last dose of SABA reliever medication

### **Asthma medication restrictions on unscheduled visits**

Asthma medication restrictions on unscheduled visits may not be feasible, and may be applied at the discretion of the Investigator. Timing of recent controller and reliever SABA use relative to the unscheduled spirometry should be noted in the record.

### **Asthma medication restrictions at site visits with scheduled dECG assessment**

Subjects should be instructed not to take their usual asthma controller medication prior to scheduled dECG assessment. Use of SABA should be avoided within 6 hours prior to the dECG assessment.

The medication restriction is waived for the enrolment dECG at Visit 1.

#### **7.7.2.2 Other medication restrictions**

- Use of oral or systemic immunosuppressive medication is not allowed. Topical administration of immunosuppressive medication may be allowed at the discretion of the Investigator. Please see section 3.2, exclusion criteria 14 and 17 for examples and further details.
- Receipt of live attenuated vaccines within 30 days prior to randomization and during the study, including the follow up period, is not allowed. Inactive/killed vaccines (e.g., inactive influenza vaccine) are allowed provided they are not administered within 5 days before/after any dosing visit.
- Subject should not receive allergen immunotherapy injection on the same day as the IP administration
- Subjects should not take any other excluded medications:
  - Oral or ophthalmic non-selective  $\beta$ -adrenergic antagonist (e.g., propranolol)

- five-lipoxygenase inhibitors (e.g. Zileuton) or roflumilast

A table with medication-related restrictions is presented in Appendix H.

### 7.7.2.3 Bronchial Thermoplasty

Subjects should not undergo bronchial thermoplasty during the entire study.

### 7.7.3 Other treatments

Other treatments which are considered necessary for the subject's safety and well-being, may be given at the discretion of the Investigator. If any such treatments include medications other than those described above, these medications are to be recorded in the appropriate section of the eCRF.

## 8. STATISTICAL ANALYSES BY ASTRAZENECA

### 8.1 Statistical considerations

The main objectives of this study are to show efficacy of tralokinumab vs. placebo in two populations, the all-subjects and a biomarker positive population, with regards to asthma exacerbations (primary) and asthma control (key secondaries).

There are two pre-specified populations studied in this study; the all subject populations and the biomarker positive population. The all subject population is the same as that studied in another pivotal study (D2210C00007) run in parallel. The biomarker positive population is not defined at the finalization of the clinical study protocol for this study, but will be defined based on results from study D2210C00007. The statistical analysis plan will be updated with this definition before the unblinding of the current study (D2210C00008).

With regards to the key secondary objectives around asthma control; to show increased asthma control for tralokinumab vs. placebo the following is considered necessary:

1. With regards to the key secondary objectives around asthma control; to show increased asthma control for tralokinumab vs. placebo the following is considered necessary: an significant effect in percent change from baseline in pre-dose/pre-BD FEV1 at Week 52 vs. placebo **and**
2. Either a significant effect in mean change from baseline in bi-weekly mean daily asthma symptom score (combined daytime and night-time score as captured in the Asthma Daily Diary) at Week 52 **or** A significant mean change from baseline in Standardised AQLQ(S) +12 Total score at Week 52.

Asthma control for a dosing regimen is only to be considered when a significant effect with regards to annualised asthma exacerbation rate up to Week 52 has been shown.

Significant results in both the key secondary outcome variables for FEV1 and ACQ-6 could give additional support for increased asthma control.

A comprehensive Statistical Analysis Plan (SAP) will be prepared prior to first subject randomized and any subsequent amendments will be documented, with final amendments completed prior to unblinding of the data. Analyses will be performed by AstraZeneca or its representatives.

All personnel involved with the analysis of the study will remain blinded until the database is locked and all protocol violations are identified.

## 8.2 Sample size estimate

The total study sample of 770 subject (385 subjects per group) are considered sufficient to show a reduction in annualised asthma exacerbation rate for tralokinumab, versus placebo in the overall study population.

Sample size calculations in terms of number of subject years needed is based on an assumed annual exacerbation rate in the placebo group of 0.8, and shape parameter of 0.95 (over-dispersion) in both the all-subject and biomarker positive population. The calculations are made for a 1% significance level for all subjects and a 4% significance level for the biomarker positive population. The methodology used described in [Keene et al 2007](#).

Assuming a uniform loss to follow-up of 15% during the study, 770 randomized subjects are expected to provide approximately 355 subject years at risk per treatment group. This is expected to provide at least 90% power for showing superiority with effects down to 37% asthma exacerbation rate reduction in the all-subject population.

The proportion of subjects in the all-subject population falling within the biomarker positive subpopulation will depend on the biomarker positive criteria to be defined in the SAP before un-blinding of this study. Based on results from study D2210C00007, the testing strategy for this study has been revised to use a 5% significance level based on the biomarker positive population as the primary population, and it is estimated that approximately 20% to 35% of the studied subjects will fulfil the biomarker positive criteria. Using a 5% significance level for the biomarker positive population as the primary population, a true asthma exacerbation rate reduction of 50% would have a power between 70% and 90% to show superiority.

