## Statistical methods

The primary analysis of the efficacy endpoints will include all data captured during the double blind treatment period. The statistical analyses will compare tralokinumab to placebo in both populations. The biomarker positive population is not defined at the finalization of the clinical study protocol for this study, but will be defined based on results from study D2210C00007 that is run in parallel before the unblinding of this study.

A hierarchical testing strategy will be applied for the confirmatory testing of primary and key secondary endpoints over the two populations to allow for control of type I error.

The primary efficacy objective will be evaluated through the null hypothesis test  $H_0$ : rate ratio (tralokinumab/placebo) equals 1 vs.  $H_1$ : rate ratio not equal to 1. The test will be based on a negative binomial model. Covariates and factors included in the model will include at least treatment and the stratifying variables.

Key secondary outcome variables will be analyzed using a repeated measures analysis approach including at least treatment and stratifying variables as the explanatory variables.

A total of 770 subjects are considered sufficient to show a reduction in annualised asthma exacerbation rate for tralokinumab compared to placebo in the overall study population.

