Sample size calculations in terms of number of subject years needed is based on an assumed annual exacerbation rate in the placebo group of 0.8, and shape parameter of 0.95 (over-dispersion) in both the all-subject and biomarker positive population. The calculations are made for a 1% significance level for all subjects and a 4% significance level for the biomarker positive population. The methodology used is described in Keene et al 2007. Assuming a uniform loss to follow-up of 15% during the study, 770 randomized subjects are expected to provide approximately 710 subject years at risk. This is expected to provide at least 90% power for showing superiority with effects down to 37% asthma exacerbation reduction rate in the all-subject population. The proportion of subjects in the all-subject population falling within the biomarker positive subpopulation will depend on the biomarker positive criteria. Based on results from study D2210C00007, the testing strategy for this study has been revised to use a 5% significance level based on the biomarker positive population as the primary population, and it is estimated that approximately 20% to 35% of the studied subjects will fulfil the biomarker positive criteria. Using a 5% significance level for the biomarker positive population as the primary population, a true asthma exacerbation rate reduction of 50% would have a power between 70% and 90% to show superiority.

All safety parameters will be analyzed descriptively. The safety analyses will be based on the safety analysis data set, defined as all subjects who received at least 1 dose of investigational product.

|  | PAGE |
|--|-------------|
| PROTOCOL SYNOPSIS.....   | 2           |
| TABLE OF CONTENTS.....   | 9           |
| LIST OF ABBREVIATIONS AND DEFINITION OF TERMS .....  | 16          |
| 1. INTRODUCTION .....  | 20          |
| 1.1 Background and rationale for conducting this study .....   | 20          |
| 1.2 Rationale for study design, doses and control groups.....  | 21          |
| 1.3 Benefit/risk and ethical assessment.....   | 22          |
| 1.4 Study Design .....   | 23          |
| 2. STUDY OBJECTIVES.....   | 26          |
| 2.1 Primary objective .....  | 26          |
| 2.2 Secondary objectives .....   | 26          |
| 2.3 Safety objectives .....  | 28          |
| 2.4 Exploratory objectives .....   | 29          |

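### The all-subjects power statement in Section 8.2 and the synopsis still rests on the superseded 1% level and ignores the gate that Section 8.5.1 puts before that test

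*Protocol*

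**What the plan says.** Section 8.2 opens by saying that 770 subjects, 385 per group, "are considered sufficient to show a reduction in annualised asthma exacerbation rate for tralokinumab, versus placebo in the overall study population". The synopsis (Statistical methods) says the same: "770 subjects are considered sufficient to show a reduction in annualised asthma exacerbation rate for tralokinumab compared to placebo in the overall study population".

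Both places then give the basis: "The calculations are made for a 1% significance level for all subjects and a 4% significance level for the biomarker positive population". On that basis Section 8.2 states "at least 90% power for showing superiority with effects down to 37% asthma exacerbation rate reduction in the all-subject population", and the synopsis states "at least 90% power for showing superiority with effects down to 37% asthma exacerbation reduction rate in the all-subject population".

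Both go on to report a change: "the testing strategy for this study has been revised to use a 5% significance level based on the biomarker positive population". Power is then restated for that population alone, with 20% to 35% of subjects expected to be biomarker positive: "a true asthma exacerbation rate reduction of 50% would have a power between 70% and 90% to show superiority".

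Section 8.5.1 sets out the testing order now in force. Steps 1 to 4 test the exacerbation rate, FEV1, AQLQ(S)+12 and ACQ-6 in the biomarker-positive population, each at two-sided 0.05, and testing stops at the first failure. The all-subjects exacerbation rate enters at Step 5, where it shares alpha equally with the biomarker-positive symptom score, so its level is 0.025. Anything not reached is declared non-significant. The synopsis says only "A hierarchical testing strategy will be applied for the confirmatory testing of primary and key secondary endpoints over the two populations". Its objectives table does label biomarker positive the primary population and all subjects the secondary one.

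**The concern.** No test at 1% or 4% exists in Section 8.5.1. The all-subjects power statement therefore describes a test the study no longer performs: the level is different, and the test is no longer available whatever happens in the biomarker-positive population. The sentence calling 770 subjects sufficient for the overall population was carried forward unchanged beside it.

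The two mismatches pull in opposite directions. Moving from 0.01 to 0.025 raises the power of the all-subjects test taken alone. Placing it behind four other tests lowers the chance that it yields a confirmatory result. A reader who takes the 90% as the chance of an all-subjects claim will be too optimistic. All subjects still form part of the primary objective (Section 2.1), so the statement is likely to be read.

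**Working it through.** **Inputs, all from Section 8.2 unless noted.** Placebo rate 0.8 per year; over-dispersion k = 0.95; 385 per group; 15% uniform loss to follow-up; about 355 subject-years per group; 37% reduction in all subjects (rate ratio 0.63); 50% reduction in biomarker positive (rate ratio 0.50); prevalence 20% to 35%. Two-sided tests (Section 8.5). Levels 0.01 (Section 8.2), 0.025 and 0.05 (Section 8.5.1).

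**Formula.** Wald test on the log rate ratio under a negative binomial model:

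- V = [1/(0.8t) + 1/(0.8t × RR) + 2k] / n, with n subjects per group and mean follow-up t years
- power = Φ(|ln RR| / √V − z), with z = 2.576, 2.241 and 1.960 for 0.01, 0.025 and 0.05

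Uniform loss of 15% gives t = 1 − 0.15/2 = 0.925, and 770 × 0.925 = 712 subject-years, against 710 in the synopsis. The sizing paper that the protocol cites is not at hand, so a second version with n = 355 and t = 1 shows how far the results depend on method.

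**1. Reproduce the stated figure (RR 0.63, level 0.01).** V = (1.351 + 2.145 + 1.900)/385 = 0.01402, √V = 0.1184, |ln 0.63| = 0.4620, ratio 3.903. Power = Φ(3.903 − 2.576) = 90.8%. With n = 355 and t = 1 it is 89.7%. The stated figure reproduces, and it belongs to the 1% level.

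**2. Same test at the current level, 0.025.** Φ(3.903 − 2.241) = 95.2%; with n = 355, 94.5%. The smallest reduction with 90% power moves as follows:

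| Level | n = 385, t = 0.925 | n = 355, t = 1 |
|---|---|---|
| 0.01 | 36.6% | 37.1% |
| 0.025 | 33.8% | 34.3% |

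**3. Step 1 at a 50% biomarker-positive reduction, level 0.05.** |ln 0.50| = 0.6931.

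- 20% prevalence: n = 77, V = (1.351 + 2.703 + 1.900)/77 = 0.07733, ratio 2.493, power Φ(0.533) = 70.3%
- 35% prevalence: n = 134.75, V = 0.04419, ratio 3.297, power Φ(1.338) = 90.9%

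The 355-based version gives 69.0% and 90.2%. This reproduces the protocol's 70% to 90%. With n = 385 and t = 0.925, power reaches 90% only at about 34% prevalence.

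**4. Consequence of the gate.** An all-subjects claim requires Step 1 to succeed, so P(claim) ≤ P(Step 1 succeeds). Under the protocol's own 50% assumption the bound is 70% to 90%.

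**5. Step 1 if the reduction is 37% in everyone (an assumption).** With n = 77: V = (1.351 + 2.145 + 1.900)/77 = 0.07008, ratio 1.745, power Φ(−0.215) = 41.5%. With n = 134.75: V = 0.04005, ratio 2.309, power Φ(0.349) = 63.6%. The 355-based version gives 40.4% and 62.3%. The bound is about 40% to 64%.

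**6. Steps 1 and 5 together.** A normal-approximation simulation (400,000 draws, 355 subject-years per group, Steps 2 to 4 taken as certain) gave 40% to 61% for a uniform 37% reduction. With 50% in biomarker positive and 33% in the rest, also assumed, it gave 67% to 88%. The first figure is the 20% prevalence case and the second the 35% case. Steps 2 to 4 can only lower these results; the protocol gives no effect sizes or standard deviations from which to say by how much.

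**The case against.** The case for leaving the text alone has substance.

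- **The revision is disclosed.** Both places say the strategy changed, Section 8.5.1 alone sets the testing rule, and the synopsis labels the populations primary and secondary. A careful reader can see that the 1% no longer applies. This stands: nothing is concealed. But the disclosure stops at the biomarker-positive population, and neither place gives 0.025 or says that the all-subjects test is conditional.
- **The 1%/4% text records how 770 was chosen.** This edition is dated 9 June 2017 and completion is planned for Q3 2017. With 52 weeks of treatment, randomization would have ended by about Q3 2016, so the sample was already fixed. Keeping the original basis is reasonable; it needs a label saying so.
- **The figure is ordinary marginal power for one endpoint.** This also stands. The protocol nowhere calls it the chance of a claim through the hierarchy.

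Stronger readings are tempting, and the documents do not support them. A reader might infer that the change of level makes the stated power too high; the opposite is true, because 0.025 is less strict than 0.01. A reader might infer that the study is undersized or that type I error is not controlled; neither follows from this point, and the Step 1 power reproduces. Nor is 70% to 90% a general ceiling: it holds under the assumed 50% biomarker-positive reduction and moves with that assumption.

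**Conclusion.** Wrong as written, minor. The all-subjects power statement and the sufficiency sentence were not brought into line with Section 8.5.1. As stand-alone power, at least 90% at a 37% reduction is still true and now conservative. It does not describe how likely the current hierarchy is to deliver a confirmatory all-subjects result, which is bounded by Step 1 power under the same assumed effects.

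These figures rest on the protocol's placebo rate, over-dispersion, loss to follow-up and prevalence range, and on a Wald approximation. The choice of person-time convention moves the powers by one or two percentage points and the 90% threshold by about half a point. The uniform 37% scenario is illustrative only. No figure is claimed for Steps 2 to 4.

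**What to change.** In Section 8.2 and the synopsis:

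1. Label the 1%/4% calculation as the original sizing basis for 770 subjects, since superseded.
2. Give stand-alone all-subjects power at the current two-sided 0.025: about 95% at a 37% reduction, with 90% reached at a reduction of roughly 34% (33.8% to 34.3% depending on method). The sponsor should confirm these with its own sizing method.
3. State that this test is performed only if Steps 1 to 4 succeed, so the chance of a confirmatory all-subjects claim is capped by Step 1 power under the same assumed effects.
4. Reword the sentence calling 770 subjects sufficient for the overall population so that it refers to stand-alone power and to that condition.

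The cost is a few sentences in two places. No subjects, procedures or analyses are added.
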